- ii. Participant will gently pull off any reflective markers that were directly mounted
- iii. A researcher will help to remove any base plate mounted markers mentioned in step f.i-f.ii
- iv. A researcher will check to confirm all markers and medical tape have been removed removed
- v. The participant will use an alcohol pad (as shown in Fig. 4) to clean where any tape had made direct contact with skin.
- o. Protection harness removing
 - i. A researcher will disconnect the harness from the mounting points highlighted in fig 5
 - ii. The participant will undo the velcro straps and remove the harness
 - iii. A researcher will take the harness and clean it using alcohol wipes and spray before putting it away.
- p. EMG removal (optional)
 - i. This is done following the procedure mentioned in visit 2, step c.
- q. ABC score
 - i. Participants will be given the Activities-specific Balance Confidence survey, included in "27067 group 1 - abc score.pdf", to self report their confidence in not losing balance while performing various different daily activities.
 - r. Discuss the participants about their expectation of the next visit
 - i. A researcher will describe what will be done in the next visit and ask the participants to inform the research team if any issues are noticed.
- 4. Fifth and sixth visits: these visits are dedicated to have the participants trained to regain muscle coordination, which is critical to use the powered prosthetic ankle. All the participants will go through these trainings. Based on whether the participants are selected as the powered prosthetic group (Group A) or the passive group (Group B), the participants will finish this training with the powered prosthetic leg or a passive prosthetic leg.
 - a. EMG mounting
 - i. This is done following the procedure mentioned in visit 2, steps b.ii - b.vii.
 - ii. Group A will have to go through this procedure.
 - b. Protection harness mounting
 - i. This is done following the procedure mentioned in visits 3-4, step 3.
 - c. Muscle coordination training
 - i. The participant is seated in a chair (standard height) while wearing their prescribed passive prosthesis with the heel of their prosthetic foot in contact with the ground to minimize knee movement.
 - ii. A computer monitor will be positioned in front of the participant at eye level as seen in Fig 14a.
 - 1. The monitor will display a UI as depicted in Fig 14b.

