 - 2. A brief 1 minute training period will be given, where the participant will be able to see their EMG recordings as well as how those signals affect and move the cursor on the UI.
 - iii. Participant will be asked to perform the following control tasks.

1. For task 1, Participant must change the color of as many blocks as possible from white to blue— when the cursor entered the boundaries of a block, the block turned blue and remained blue for the duration of the task.
 - a. Each trial will last about 1-3 minute.
 - b. Participant is given 3 minutes of rest between each trial
 - c. The task will continue until performance is “saturated”, i.e. the subject was unable to acquire more than one new block per minute, or after 5 trials.
2. For Task 2, we changed the shading of the blocks that the subjects reached in Task 1 to a blue gradient scaled to the cumulative number of frames the cursor entered a block. When the cumulative number of frames reached a preselected number (about 500 usually), we changed the block color to a distinctly different navy blue color.
 - a. The blocks that the subject was not able to reach during Task 1 were colored gray and there was no incentive to try and expand the reachable control input space.
 - b. The task will continue until performance is “saturated”, i.e. the subject is unable to acquire more than one new navy blue block per minute, or until the end of the task.
- iv. After completing the control tasks, these 2 tasks may be repeated while the participant is standing on the treadmill while wearing the safety harness and with access to handrails for support. This is to ensure the participant has a clear understanding of the input-output relationship between their residual limb and the device while both seated and standing.

[figure not shown]
[figure not shown]

Fig. 14: A) Amputee subject seated while looking at computer monitor with knee at a comfortable angle with heel of prosthesis resting on the floor. B) Real-time visual feedback display where control goal is to change as many blocks from white to blue as possible. Block turns blue when computer cursor enters boundaries of the block

- d. Prosthetic/virtual ankle control
 - i. Participant will wear either their own passive device or the dEMG prosthesis.
 - ii. For the passive device, the participant will be seated while they practice using EMG to control a virtual ankle, as seen in Fig 15b displayed on a screen set in front of them at eye level.

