 - iii. For the dEMG device, the participant will be asked to control the powered ankle while seated as seen in Fig 15c.
 - iv. For both groups EMG activation for TA and GAS will be displayed for the participants.
 - v. For both groups, after they have practiced EMG control while sitting down they will repeat the exercise while standing. A walker will be used in stance as needed to support the participant's balance while they practice the ankle control as seen in Fig 15d.

- e. Ankle posture test
 - i. The participant sits in a chair comfortably. Two virtual ankles are displayed on a screen. One shows the expected position of the ankle and

one shows the current position of the ankle joint. The participant will use the EMG signals measured from their residual limbs to adjust the position of the virtual ankle to meet the referenced one.

- ii. For each trial, the reference ankle will start at the neutral position (both muscles are relaxing) and the ankle angle follows a sinusoid trajectory, which covers the ankle range of motion. The sinusoid signal will last five cycles for each trial and the frequency is set as 0.25, 0.5, 0.75, and 1Hz.
- iii. Participants will go through maximum 20 trials with a 2 minute break in every four trials. The trial also stops when the participants are able to meet the requirement in the highest frequency.
- iv. For participants, who will use the powered prosthetic foot, the procedure will be repeated with the powered prosthetic ankle as the output instead of the virtual ankle. For participants, who will use the passive foot, the PT will move the contralateral foot gently, and ask the participant to follow the virtual ankle to follow the movement of the contralateral ankle.

- f. Protection harness remove
 - i. This is done following the procedure mentioned in visit 3-4, step o.
- g. EMG electrodes remove (Group A only)
 - i. This is done following the procedure mentioned in visit 2, step c.
- h. Discuss the participants about their expectation of the next visit
 - i. A researcher will describe what will be done in the next visit and ask the participants to inform the research team if any issues are noticed.

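### Visits 5-6 assign EMG electrode mounting and removal to Group A, yet all three training blocks in those visits need live EMG from Group B as well

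*Protocol*

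**What the plan says.** All of this is in the Protocol, under the fifth and sixth visits.

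- **Introduction.** Participants are to be "trained to regain muscle coordination, which is critical to use the powered prosthetic ankle". Both groups are included: "All the participants will go through these trainings". Group A (powered) and Group B (passive) differ in the prosthesis they train with.
- **Step a, EMG mounting.** The visit 2 mounting procedure is invoked, followed by one line on who undergoes it: "Group A will have to go through this procedure". Group B is not mentioned.
- **Step c, muscle coordination training.** In a short familiarisation period "the participant will be able to see their EMG recordings as well as how those signals affect and move the cursor on the UI". Step c.i seats the participant in their own passive prosthesis, and no group is exempted.
- **Step d, prosthetic or virtual ankle control.** Step d.ii: "For the passive device, the participant will be seated while they practice using EMG to control a virtual ankle". Step d.iv: "For both groups EMG activation for TA and GAS will be displayed for the participants". Step d.v: "For both groups, after they have practiced EMG control while sitting down they will repeat the exercise while standing".
- **Step e, ankle posture test.** Step e.i has the participant position the virtual ankle with residual-limb EMG. Step e.iv gives a variant for passive-foot users, so Group B is expected to be there.
- **Step g.** The heading restricts removal: "EMG electrodes remove (Group A only".

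**The concern.** The set-up and take-down lines describe visits in which only Group A wears electrodes. The training between them describes visits in which both groups do. A member of staff who follows the set-up lines cannot deliver Group B's training. One who delivers the training must fit electrodes that the removal step does not cover for Group B.

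The statistical stake arises on the first reading only. The protocol treats this muscle coordination training as critical to using the powered ankle. The introduction to visits 7-11 says that all participants train so that the contribution of training to any change in performance is taken into account. Comparable training is therefore part of the protocol's own control. If Group B receives no EMG training at visits 5-6, a Group A versus Group B difference reflects the device and the presence or absence of that training together. Testing everyone on both devices at visits 12-13, and again at visits 14-15, would not remove this, because Group B would come to its powered-ankle evaluations without the training.

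**Working it through.** The protocol gives no figure on this point to reproduce, so the check sets the steps side by side and then counts.

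**Does each step in visits 5-6 need EMG from Group B?**

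| Step | Who is covered | EMG from Group B? |
|---|---|---|
| a.ii mounting | Group A named, Group B not mentioned | Not provided for |
| c.ii.2 cursor training | All, no exception stated | Needed |
| d.ii virtual ankle | Passive-device users explicitly | Needed |
| d.iv muscle activation display | Both groups explicitly | Needed |
| d.v standing repeat of EMG control | Both groups explicitly | Needed |
| e.i ankle posture test | All, no exception stated | Needed |
| g removal | Group A only, explicitly | Excluded |

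Two set-up lines (a.ii, g) stand against five EMG instructions. Three of the five name passive users or both groups (d.ii, d.iv, d.v). Two cover Group B because the introduction includes everyone and no exception is made (c.ii.2, e.i).

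**Can either reading satisfy every line?**

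1. *Steps a.ii and g govern.* Group B has no electrodes, so there is no signal to move the cursor in c, drive the virtual ankle in d, or follow the reference in e. Blocks affected: 3 blocks × 2 visits = 6. Blocks workable without EMG: 0. Group B has EMG training at 0 of 2 visits.
2. *Blocks c to e govern.* Group B is fitted and trains at 2 of 2 visits. Step a.ii can bear this, since it does not say that only Group A is mounted. Step g cannot, because it reserves for Group A the removal procedure of visit 2 step c, which includes the skin check and cleaning. The general rule in the risk section, skin inspection before and after electrode use, would still apply.

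Neither reading lets all the steps be followed for Group B.

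**Does other text resolve it?** No. Visits 3-4 confine mounting to the powered-prosthesis visit, and visits 7-11 step a ties it to powered-prosthesis users. Both match the restrictive wording of a.ii and g, but in visits 5-6 the passive group's own training needs EMG.

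**Training content at stake per Group B participant, as maxima.**

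- Task 1 in block c: up to 5 trials per visit before any standing repeat; 5 × 2 = 10 if run in full at both visits.
- Ankle posture test in block e: up to 20 trials per visit; 20 × 2 = 40 if run in full at both visits.

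**Participants.** The planned number is 50. The allocation ratio is not stated; at 1:1, 50 / 2 = 25 are in Group B.

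**Fittings already planned for Group B.** Visit 2 gives 1, and the powered visit in each of the pairs 3-4, 12-13 and 14-15 gives 3, so 1 + 3 = 4. Adding visits 5 and 6 gives 4 + 2 = 6, if no visit is skipped.

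**The case against.** The strongest reply is that this is a drafting slip that would show itself at once. With no electrodes the cursor does not move and the virtual ankle does not respond, so staff would notice and fit Group B, as they already did at visit 2. That makes the harmful reading less likely. It does not settle what the protocol requires, and staff who notice the problem must still depart from a written line. The restrictive wording also matches the pattern in visits 3-4 and 7-11, so following it would be a natural mistake.

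Step a.ii does not say that only Group A is mounted. That is true, and taken alone it is not a contradiction. The conflict is firmest in step g, which does say so.

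The removal gap carries little practical weight: the electrodes are cabled to the recording system, a removal procedure exists in visit 2, and the skin-inspection rule is general. This is largely right, and the gap matters mainly because it shows that the second reading also fails.

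The groups train differently by design: Group A also controls the powered ankle, Group B a virtual one, and visits 7-11 use the prosthesis of the assigned group. So the comparison already combines device with some training differences. That stands, but under blocks c to e both groups receive EMG training. Losing it in one group is a further difference that the design does not intend.

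Finally, clinicians may recommend skipping visits or tasks, so the trial and fitting counts are upper limits. They are given as such.

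**Conclusion.** The concern holds. In visits 5-6, steps a.ii and g cannot be reconciled with blocks c, d and e for Group B. The range for Group B runs from EMG training at 0 of 2 visits, if the set-up lines are followed, to 2 of 2 visits with removal unassigned, if the training text is followed. All 3 training blocks are affected at each visit.

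The training text suggests that blocks c to e are intended and that the two set-up lines were left behind. The mixing of device and training arises only if staff follow those lines. The figure of about 25 participants assumes 1:1 allocation, and the trial counts assume that the blocks are run in full at both visits. The contradiction itself depends on neither assumption. It should be fixed: the conflict is certain, its effect on the comparison depends on which lines are followed, and the correction is cheap.

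**What to change.** Amend two lines in visits 5-6:

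- **Step a.ii:** state that EMG mounting (visit 2, steps b.ii to b.vii) applies to both groups.
- **Step g:** delete the Group A limit and state that removal (visit 2, step c) applies to both groups.

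As a secondary clarification, reword visits 7-11 step a. There, optional probably means where applicable, as it appears to in visits 3-4 step p. As it stands, the line could be read as allowing the EMG-controlled ankle to be used without EMG. The main point does not depend on this.

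The cost is a wording amendment plus electrode set-up and removal time for Group B at two visits. No new procedure is introduced: fittings for a Group B participant who attends every visit rise from 4 to 6.

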Project Title:

Toward Restoration of Normative Postural Control and
Stability using Neural Control of Powered Prosthetic
Ankles

Protocol Number: 26076

Protocol is approved by NC State University IRB

Approval Period:

07/14/23 – 07/13/24

Updated on: 03/18/2024

Number of Participants:

- 50 unilateral transtibial amputees (below the knee amputation)

Inclusion/Exclusion:

- AMPUTEE ELIGIBILITY
 - 18 years or older
 - unilateral bower limb amputee
 - K-level 2 or higher (who are frequent prosthesis users and may benefit from the proposed prosthesis training and use of dEMG controlled powered prosthesis)
 - Amputation occurred over 2 years ago
 - At least 1 year of experience using their prosthetic leg
 - Has used the current socket for at least 6 months without a significant skin issue or major modification.
 - Are willing to come to NC State University's Centennial Campus to participate in research and be photographed while doing research activities
- AMPUTEE INELIGIBILITY
 - have a very short residual shank (the length of the residual limb is $\leq 15\%$ of the length of intact limb)
 - cannot perform functional ambulation in the community on a daily basis without assistive devices
 - Cognitive or visual impairment that affects the participant's ability to provide informed consent or to follow simple instructions during the experiments
 - Congenital amputees
 - Amputees who use powered prosthetic ankles
 - Weight more than 300lbs
 - Pregnant Person
 - Allergic to latex, which is often contained in medical tapes.
- Reasons for the inclusion and exclusion criteria:
 - We would like to involve participants, who are capable to walk in the community without additional assistive devices.
 - To ensure that there is enough muscles on their residual limb for EMG data collection, we would like to exclude those who have very short residual limbs. Congenital amputees are also excluded due to the fact that they may never develop the needed muscle patterns on their residual limb.
 - To ensure their safety, we need them to have a healthy residual limb with low risk of pressure ulcer (young amputees, pregnant people, and recent amputees usually have high risk of pressure ulcers).
 - Users of powered prosthetic ankle is excluded due to the fact that they could not be used for the comparison group and may cause bias in the randomization.
 - The safety harness has a limit of 300lbs, which is used to limit the maximum weight of the participants.

Recruitment:

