5. Seven – eleventh visits: These visits are designed to give participants needed training, so participants are able to integrate the action of the powered prosthetic ankle with their full body motion for various tasks. To ensure that contribution of the training procedure to the performance changes are considered, all the participants will go through the training with the prostheses aligned with their group.

- a. EMG mounting (optional for patients use the powered prosthesis)
 - i. This is done following the procedure mentioned in visit 2, steps b.ii - b.vii.
- b. Protection harness mounting
 - i. This is done following the procedure mentioned in visits 3-4, step 3.
- c. Transition between sit and standing
 - i. The participant will start the task seated in a chair.
 - ii. The participant will be asked to lean forwards and stand up from the chair, using the armrests for support if needed.
 - iii. The participant will remain in the standing position, standing up right with back straight, for a few seconds.
 - iv. The participant will be asked to then transition from standing back to sitting in the chair.
 - v. This process will repeat for up to twenty trials. The participant will be offered the chance to rest for 2-3 minutes after 10 trials finished.

[figure not shown]

Fig 16: setup of the transition between sit and standing

- d. Single limb balance
 - i. While wearing the safety harness, the participant will begin by standing on the treadmill with feet shoulder width apart, with one foot on each of the treadmill belts.
 - 1. Handrails will be positioned on either side of the treadmill to use for support as shown in Fig. 9.
 - ii. Participant will be asked to raise their non-prosthetic foot off the ground and to balance on their prosthetic side as long as they are comfortably able to do so.
 - iii. The trial will end either when the participant's non-prosthetic foot touches the ground, or when the participant needs to use a handrail for support.
 - iv. Between trials a stool will be provided to allow the participant to sit and rest until they are ready to resume.
 - v. The trial will repeat 10 times..
- e. Squats
 - i. The participant will stand on the treadmill with feet shoulder width apart, toes facing forward, and one foot on each belt of the treadmill.
 - ii. The participant will be asked to raise their arms out in front of them and slowly bend their knees and lower their body towards the ground while keeping their back straight and chest lifted

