- 6. Twelfth-thirteenth visit (duplicate of Third and fourth visit). These visits are used to evaluate the impact of the training program on the performance of the participants to conduct tasks which are not included in the training procedure. Each participant will conduct the task with both passive and powered prosthetic legs on different days.
- 7. Fourteenth-fifteenth visits (duplicate of Third and fourth visit). These visits are used to understand the long term effects of the training program on the participants. These visits will be conducted three months after the 13th visits.

Devices Used in the Research:

- Powered ankle prosthesis
 - This is a custom built minimal risk device shown in Fig. 1.
 - The device is designed so that no moving parts are directly attached to the user's prosthetic socket.
 - This minimizes risk of personal injury and damage to the socket
 - The procedure for putting on this device is described in the second visit, step a.
 - Safety precautions, such as the fall prevention suit and handrails used throughout the study, will ensure the risk of falls while using the device is minimal.
- Disturbance system
 - This is a custom built minimal risk device illustrated in Fig. 11.
 - The system is securely attached to the ceiling minimizing risk of it falling and causing damage
 - The weight used to generate the disturbance will never exceed 10% of the participant's body weight, minimizing risk that the disturbance will cause the participant to fall or stumble.
 - A light will flash before the disturbance occurs, ensuring the participant isn't caught off guard by the disturbance and can brace accordingly.
- Fall prevention suit
 - This device is off the shelf by not a medical device
 - This device is used on label and as approved

- This device is being used simply as a tool for fall prevention.
 - The procedure to put on this device is shown in Fig. 5.
- Instrumented treadmill (Registered Establishment Number: 1530895)
 - The device is off the shelf
 - The device is used on label and as approved
 - The device is being used simply as a tool for data collection in the research
 - The device is fixed on the ground and the participants will step on it after the treadmill is powered up. The participants will step off before the treadmill is powered off.
- VICON motion capture system (Registered Establishment Number: [1000377231](#))
 - The device is off the shelf
 - The device is used on label and as approved

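### All participants are trained and retested alike, so visits 12-15 cannot show the effect of the training program; the only controlled training contrast is powered versus passive training

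*Protocol*

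**What the plan says.** The visit-by-visit part of the protocol sets up the following.

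- **Baseline (item 3, third and fourth visits).** Each participant is tested once on their own passive prosthesis and once on the powered ankle, in random order.
- **Training, visits 5-6 (item 4).** "All the participants will go through these trainings". What differs is the device: depending on group, "the participants will finish this training with the powered prosthetic leg or a passive prosthetic leg". Group A is powered and Group B is passive.
- **Training, visits 7-11 (item 5).** The rule again covers everyone: "all the participants will go through the training with the prostheses aligned with their group". The reason the protocol gives for it is this: "To ensure that contribution of the training procedure to the performance changes are considered".
- **Post-training tests (item 6, visits 12-13).** These duplicate visits 3-4, again on both prostheses. "These visits are used to evaluate the impact of the training program on the performance of the participants".
- **Follow-up tests (item 7, visits 14-15).** These are a further duplicate, three months after visit 13. "These visits are used to understand the long term effects of the training program on the participants".

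No group is tested without being trained, and no delayed or sham training is described. The reasons for the eligibility criteria do refer to a comparison group and to randomisation: users of powered ankles are excluded because "they could not be used for the comparison group and may cause bias in the randomization".

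**The concern.** The purpose given for visits 12-15 is the effect of the training program. To learn that, one must know how participants would have scored at those visits without training. The protocol contains no one who could show this.

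The change from visits 3-4 to visits 12-13 combines several things: training, having done the battery before, and the passage of time. On the powered ankle it also includes growing familiarity with a new device. Visit 2 only mounts the ankle and checks the electrodes, so visits 3-4 contain its first scored use. They also come before the coordination training that item 4 describes as critical to using it.

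Item 5 presents training everyone as the way to take account of training. It does balance training between the groups. A factor given equally to both groups drops out of their comparison, however, so this step removes the common training effect from view and does not measure it.

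At stake is the conclusion the trial may draw. A statement that the program improves balance or mobility would have no controlled support, whatever the data show.

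**Working it through.** **1. What can be identified.** The protocol gives no figure to reproduce here. For one test prosthesis and one follow-up time, let T be the training effect common to both groups, R the effect of repeat testing, familiarity and time, and D the additional effect of training on the powered instead of the passive prosthesis. Then:

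- mean change in Group A = T + R + D
- mean change in Group B = T + R
- difference, A minus B = D

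There are two equations and three unknowns. D is identified. T and R appear only as a sum, and more participants would not separate them.

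The full layout gives the same answer. Two groups, two test prostheses and three times make 12 cell means. The model has an intercept and a prosthesis effect, plus a retest term, a common training term and an A-minus-B term for each of the 2 × 2 combinations of follow-up time and test prosthesis. That is 2 + 3 × 4 = 14 parameters. The design matrix has rank 10, which is 2 + 2 × 4, because one parameter is lost in each of the four combinations. The A-minus-B terms and the prosthesis contrast are estimable. The common training terms and the retest terms are not.

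**2. How far a pre-post reading could mislead (illustration).** Suppose a pre-post change were tested with a paired t-test at two-sided 5%, and training did nothing.

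Inputs:
- n = 50 is the protocol's total.
- n = 25 assumes an equal split; the protocol gives no allocation ratio.
- The repeat-test gain g (in SD units) and the pre-post correlation r are assumptions.

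Formulas: the standard error of the mean change is √(2(1 − r)/n), and the noncentrality is g divided by that standard error. The probability of significance comes from the noncentral t distribution with n − 1 degrees of freedom.

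Example: g = 0.3, r = 0.7, n = 25. The standard error is √(0.6/25) = 0.155, the noncentrality is 0.3/0.155 = 1.94 and the critical value is 2.06. The probability is 46%. At n = 50 the standard error is √(0.6/50) = 0.110, the noncentrality is 2.74 and the probability is 77%.

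| Assumed gain g | n = 25, r from 0.6 to 0.8 | n = 50, r from 0.6 to 0.8 |
|---|---|---|
| 0.1 SD | 8% to 12% | 12% to 20% |
| 0.2 SD | 19% to 33% | 34% to 59% |
| 0.3 SD | 36% to 62% | 64% to 91% |

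A repeat-test gain shared by both groups cancels in the A-minus-B difference in change. If D is zero, that comparison keeps its 5% error rate.

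**3. Follow-up visits.** The same identification argument applies to visits 14-15. In addition, the protocol describes no use of the powered ankle between visits 13 and 14, while the passive prosthesis is the one participants wear every day. Practice on the two devices may therefore differ over those three months. This is a further reason to compare the groups on the same test prosthesis.

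**The case against.** **The protocol prescribes no pre-post test.** This stands. A reader might infer that a pre-post gain will be reported as the effect of training. The documents do not say so: items 6 and 7 give a one-line purpose and no analysis, and the SAP is not at hand. But the point does not depend on the analysis chosen, because no SAP can supply an untrained comparator that the visit plan lacks.

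**The between-group reading is already implied.** The protocol has Groups A and B, a comparison group and a reference to randomisation, so the impact of training could mean each group's program compared with the other's. That reading is possible and would make the fix one of wording. It is not what the two purpose sentences say, and item 5's reason for training everyone suggests that the contribution of training itself is meant to be captured.

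**The design does more than compare two kinds of training.** This also stands. Every participant is tested on both prostheses at each time, which gives a valid within-person device comparison. Group B is also retested on the powered ankle without Group A's powered-device training, so it serves as a retest control for that training. The first contrast is not about training, and the second is the A-versus-B contrast.

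**Follow-up.** A reader might infer that Group A on the powered ankle will be compared with Group B on the passive foot as a measure of retention. No section proposes this, and both groups are tested on both devices.

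**The size is assumed.** Correct. The battery includes some familiarisation, such as a short sway try-out and 3-10 practice perturbations per condition, which may keep the gain small. At 0.1 SD the excess over 5% is modest.

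**Conclusion.** The concern holds as a mismatch between the stated purpose of visits 12-15 and what the design can identify. The effect of the training program, short-term or long-term, cannot be separated from repeat testing, familiarity with the powered ankle and time. This follows from the visit plan alone and needs no numerical assumption. For claims about training, the only controlled contrast is powered against passive training.

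The size is illustrative. With no training effect, a pre-post reading would be significant in about 8-62% of analyses at n = 25 and 12-91% at n = 50. This rests on assumed gains of 0.1-0.3 SD, correlations of 0.6-0.8 and, for n = 25, an equal split. It describes what would follow from that reading and not an analysis the protocol lays down.

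**What to change.** Reword items 6 and 7 so that visits 12-13 and 14-15 serve to compare training on the powered prosthesis with training on the passive prosthesis. Name the contrast: the Group A versus Group B difference in change from visits 3-4, on the same test prosthesis, taken separately for the powered and the passive test visit. State that within-group pre-post change is descriptive and will not be attributed to training. In item 5, say that training everyone balances training between the groups.

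For visits 14-15, add that no powered-ankle use is described between visits 13 and 14 while the passive prosthesis is the everyday one, and that follow-up results are therefore also compared on the same test prosthesis.

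This changes wording only and adds no visits or data. The cost is a narrower conclusion: the trial gives up the claim that the training program itself works. Keeping that claim would need a comparator that is tested but not trained.
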